In response to the IRB's decision that therapists in Trials 2 and 3 will be engaged in research activity, participation in Trials 2 and 3 will be limited to therapists within Mayo Clinic (Rochester and Health System) and external organizations that have an IRB and with which we complete a reliance agreement. Recruitment of therapists within Mayo Clinic (Mayo Clinic will be used to refer to Rochester and Health System) will be conducted by the study staff (PI, study coordinator, intervention specialists) directly through emails and phone calls (scripts included in this modification). In addition, study staff will provide the recruitment scripts to division leaders and supervisors to ensure that recruitment and participation in the study is consistent with clinical programming. Finally, the study staff will provide recruitment materials to members of the Convergence Child Specialty Council to provide interested clinicians with familiar contact to discuss the study. All efforts to recruit clinicians will emphasize the voluntary nature of the study and that declining to participate will have no effect on their employment or care through Mayo Clinic. Our study staff will directly contact external institutions that provide child mental health care to determine if they would be interested in partnering in this project. Only institutions that have at least 5 interested and appropriate therapists will be contracted with. We anticipate entering agreements with up to 4 organizations in order to enroll 30 therapists for Trial II. The Mayo Clinic IRB will serve as the IRB of record for the collaborating institutions. Recruitment of therapists within the partnering institutions will be implemented by a site-PI following the procedures consistent with those used within Mayo Clinic. Trial 3 will involve therapists from the study staff providing treatment.

Therapists that are interested in participating but are not covered by an IRB, will be enrolled in the first trial, i.e., acceptability study.

C.3.b. Phase II: Therapist Trials (18 months). The second phase of this proposal will address Aim 2 of assessing the feasibility, safety, acceptance, and impact of *Anxiety Coach* through three trials.

Note: The current modification covers the initiation of Trial 2 and Trial 3. Trial 1 has been approved and enrollment as begun.

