C.4.a. Inclusion Criteria. *Therapists:* 1) Treat child anxiety patients; 2) Current license as a mental health professional (e.g., psychologist, clinical social worker, marriage and family therapist, professional counselor); and 3) competence to provide therapy to youth based on review of institutional or state licensing records. *Patients:* 1) Youth between the ages of 7 and 17 presenting for outpatient therapy with a principal diagnosis of social phobia, separation anxiety disorder, panic disorder with and without agoraphobia, specific phobia, or obsessive compulsive disorder (based on structured interview, additional available information and consensus of [name] and evaluator); 2) A parent or other primary care giver available to participate with the child in all assessment and treatment activities; and 3) English speaking.

C.4.b. Exclusion Criteria. *Therapists:* 1) History of investigation or disciplinary action (based on review of institutional records), Trials 2 and 3 only; and 2) Opposition to CBT per survey responses. *Patients:* 1) History of and/or current diagnoses of: psychosis, autism, bipolar disorder, mental retardation, oppositional defiant disorder, selective mutism, PTSD, or major depressive disorder measured by structured interview and all available clinical information; 2) current suicidality as assessed by the depression module of the structured diagnostic interview and the CDI-S; 3) A positive diagnosis in the caregiver of mental retardation, psychosis, or other psychiatric disorders or conditions limiting their ability to understand CBT (based on clinical interview); 4) an adequate trial of CBT for the child of any psychiatric disorder based on clinical interview; and 5) Initiation or dose change of an antidepressant for the child within 8 weeks or an antipsychotic within 6 weeks of enrollment. Patients and their prescribers will be encouraged to refrain from changing psychotropic medications or dosages during the study without consulting the study staff (Human Subjects); changes will be recorded and analyzed.

C.5. Interventions. Each therapist will be randomized to treat one or two patients with TAU or FTF-AC. The general intervention structure is consistent across treatments to avoid confounding variations.

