C.6.b. Inclusion of Treatment as Usual. The inclusion of TAU provides a more stringent and naturalistic test of the relative feasibility and benefits of *Anxiety Coach* than use of no-treatment or non-specific active placebo. In addition, a TAU control group does not require training of therapists. On the other hand, although exposure is rarely used in community practice,¹⁵ it is possible that TAU may include exposure and thereby dilute the effect of the TAU vs. FTF-AC comparison. To decrease this possibility, recruitment will focus on therapists who report infrequent use of exposure. In addition, the content of TAU sessions will be recorded and coded to document the use of exposure. Other alternatives, such as a waitlist control group, non-specific active placebo, or medication would not test the impact of *Anxiety Coach* on therapist use of exposure. Practical obstacles would make it extremely difficult to provide pharmacological care in a safe manner, as the targeted population includes families living some distance from the study site.

C.6.c. Impact of Translating CBT into an ICT Platform. Because the current design does not compare *Anxiety Coach* to traditional CBT it cannot examine the costs or benefits of translating CBT to an ICT platform. Although *Anxiety Coach* has the potential to enhance patient adherence and the efficiency of CBT, given the limited availability of CBT providers, increasing reach through dissemination and minimal contact treatment addresses a more pressing need. As such, a comparison between minimal contact *Anxiety Coach* and face-to-face CBT would have less impact of increasing the reach of evidenced-based care than the proposed design.

C.6.d. Impact of *Anxiety Coach* vs. Other Treatment Aides. The current design controls for the effect of introducing ICT into therapy by including an iPod Touch to track symptoms in the TAU condition. However, the study does not compare *Anxiety Coach* to other electronic or paper treatment-aides. Such questions about the relative value of *Anxiety Coach* compared to other interventions delivered would be more appropriately addressed after the feasibility and beneficial effects of *Anxiety Coach* have been established.

C.7. Procedures

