C.7.a. Therapist Survey. A survey will be sent to all the mental health providers contracted by MMSI under IRB 14-002608. Therapists that practice in areas designated by the U.S. Department of Health and Human Services as Mental Health Care Health Professional Shortage Areas,⁷⁸ treat children with anxiety disorders, endorse openness to CBT, and report infrequent use of exposure will be recruited into the study.

C.7.b. Therapist Telephone Screening and Consent. Therapist eligibility and interest in participating in the study will be assessed through phone screening completed by the study team. Information regarding licensure status, frequency of treating children with anxiety disorders, and openness to piloting a smartphone-based CBT aide will be confirmed by the therapists' institution. Therapists that meet inclusion/exclusion criteria will be mailed a consent form.

C.7.c. Patient Telephone Screening. For Trials 2 and 3, a multi-gate screening procedure will be used to recruit patients. Interested patients evaluated as part of clinical practice by participating therapists will be an informational letter, instructions, two copies of the consent/assent documents, parent- and child-report forms, and instructions to contact the study team for pre-consent screening. Therapists will also relay patient name and information to study staff via telephone for contact. During the screening call, information regarding the

patient's symptoms, previous treatment and diagnoses, and willingness to be assigned to one of three treatment conditions will be gathered. The number of callers deemed ineligible and reasons for ineligibility will be recorded in the Screening Log. If patient is likely to be eligible, a consent and evaluation videophone visit will be scheduled. This visit should occur within 1 week (+/- 1 week) from the initial therapist visit.

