C.8.c. Recruitment. The current recruitment strategy is intended to approximate the conditions under which *Anxiety Coach* would have the most impact, i.e. areas where psychiatric needs exceed mental health providers with specialization in CBT for childhood anxiety disorders. To maximize external validity the experimental treatment will be implemented by community therapists recruited from a large geographical area, particularly areas with a mental health shortage designation, and treatment will be paid for through traditional clinical mechanisms.⁷⁸ The principle limitation of the recruitment paradigm is that only patients with access to services will be included in the study. However, this study will establish the safety and efficacy of *Anxiety Coach* with differing levels of therapeutic contact before examining *Anxiety Coach* as a no contact treatment where it would be more difficult to address problems with safety, usability, or lack of progress. We anticipate that the data from the proposed study will prepare for future projects extending services to those outside the system by: a) improving the application; b) documenting the utility of *Anxiety Coach*; and c) creating a web-based portal

through which people in need of treatment could be followed by a provider with whom they have never had face-to-face contact.

C.8.d. Treatment Protocols. For Trials 2 and 3 the guidelines for each intervention instruct the therapist to interact (face-to-face or via the web-portal depending on the condition) once per week for 6 to 12 weeks. Although therapists are not given further instructions on how to deliver *TAU*, the six-session minimum will likely result in a higher level of care than is typically received in real-world settings, since standardization of contact across the interventions is necessary to examine the ability of *Anxiety Coach* to increase provider use of exposure.

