C.9.e. Therapist Report Measures. The survey, conducted under IRB 14-002608, will be an adaptation of the measures used in a previous study¹⁵ and will inquire about demographic/practice information. Therapists will be asked to indicate whether or not they have used various interventions over the past 12 months with anxious children and adolescents (presented separately). Additionally, therapists will be asked about their beliefs about exposure. Therapists that provide study treatment will complete the exposure beliefs questionnaire again before and after treatment. The modified System Usability Scale plus AC items (mSUSplus; Bangor et al., 2008; Brooke, 2013). Therapists in all 3 trials will complete the mSUSplus. Therapist in Trial 1 will complete the SUS two weeks and six months after training. In Trials 2 and 3 therapists will complete the SUS as part of the post treatment measures.

C.9.f. Session Coding. All therapy sessions in the TAU and FTF-AC will be audio recorded and coded with a CBT for child anxiety Treatment Adherence scale that has been used in previous treatment studies,^{18,67,74} in addition to recording the amount of time spent planning and conducting exposure. Audio recording will be used rather than video, as it will be easier to set-up and transport if exposures are completed outside of the office. Electronic communication between therapists and patients will be automatically recorded and phone conversations will be summarized in writing. These contacts will also be coded for recommendations regarding exposure. 10% of sessions will be coded by two evaluators independently to examine inter-rater reliability.

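### The infrequent-exposure filter that C.6.b relies on is not carried into Trial 2 recruitment, and no linkable pre-randomisation measure of Trial 2 therapists' prior exposure use is specified

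*Protocol*

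**What the plan says.** Protocol C.6.b names exposure within TAU as a threat to the TAU versus FTF-AC comparison and gives two responses. The first is preventive: "To decrease this possibility, recruitment will focus on therapists who report infrequent use of exposure". The second is documentary: "In addition, the content of TAU sessions will be recorded and coded to document the use of exposure".

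The preventive filter also appears in the survey-based part of C.3.a.4 and in C.7.a, where therapists who "endorse openness to CBT, and report infrequent use of exposure will be recruited into the study". Section 4.1.1.c likewise treats membership of the Phase II pool as implying infrequent exposure use.

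A later part of C.3.a.4 changes the Trial 2 source after an IRB decision: "participation in Trials 2 and 3 will be limited to therapists within Mayo Clinic (Rochester and Health System) and external organizations". Those outside organisations need an IRB and a reliance agreement. Recruitment there is by direct email and telephone, through division leaders, or through a site PI.

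On measures, C.9.e says: "Therapists that provide study treatment will complete the exposure beliefs questionnaire again before and after treatment". C.10.b.2 compares therapists' exposure use between TAU and FTF-AC by ANCOVA, controlling for diagnosis and symptom severity.

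**The concern.** Trial 2 is the trial meant to show whether the app increases exposure use, and C.6.a gives this as one purpose of the TAU versus FTF-AC comparison. The protocol's only preventive step against exposure in TAU is to select therapists who rarely use it. If that step does not operate for Trial 2, therapists who already use exposure can enter either arm. Without a baseline record, the sponsor could not tell whether the arms started level on the behaviour being compared. Nor could it describe whether the app helps mainly those who rarely used exposure before. The estimates are intended to inform a fully powered trial, so an unrecognised imbalance would pass into its planning.

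**Working it through.** The protocol states no power, alpha or effect size for this comparison, so there is no figure to reproduce. The check is mainly a trace through the text.

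**1. Where the filter is stated and where it is absent**

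| Section | Infrequent-use filter? |
|---|---|
| C.3.a.4, survey route | Stated, for Phase II |
| C.6.b | Stated, as the mitigation |
| C.7.a | Stated, for the study |
| 4.1.1.c | Implied for the Phase II pool |
| C.3.a.4, later Trial 2 and 3 route | Not mentioned |
| C.4.a, therapist inclusion | Absent: "1) Treat child anxiety patients; 2) Current license as a mental health professional", then competence with youth |
| C.4.b, therapist exclusion | Disciplinary history and opposition to CBT only |
| C.7.b, telephone screen | Absent: licensure, "frequency of treating children with anxiety disorders, and openness to piloting a smartphone-based CBT aide" |

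The sections that decide who enters Trial 2 do not carry the filter.

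**2. Whether prior exposure use is available at baseline**

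- The survey asks about interventions used in the past 12 months (C.9.e). No section says that directly recruited Trial 2 therapists complete it.
- Identifiable survey answers stay with the survey center (4.1.1.b), and names are released to the study team without code numbers (4.1.2.a). An existing answer is therefore not clearly linkable to a Trial 2 therapist.
- Only the beliefs questionnaire is expressly repeated for treating therapists (C.9.e, 4.1.1.b). Its pre-treatment timing is not fixed relative to randomisation, which follows therapist consent (C.7.e). Nor is it fixed relative to training, which precedes each patient's treatment (C.5.a) and in FTF-AC demonstrates exposure exercises (C.5.c).
- Trial 1 therapists do complete the practice and beliefs material before training (C.7.g).
- The ANCOVA in C.10.b.2 has no term for prior exposure use.

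**3. What session coding supplies**

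All TAU and FTF-AC sessions are audio recorded and coded, including time spent planning and conducting exposure, with 10% double coded (C.9.f). C.7.f extends coding to communication. The SAP also describes examining exposure use by session and therapist. Exposure during TAU is therefore measured, but only after assignment.

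**4. How likely a chance imbalance is**

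Inputs: 30 therapists (C.3.b, Trial 2). A 15/15 split is assumed, because no allocation ratio is stated. K, the number of regular exposure users among the 30, is also assumed.

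P = sum of C(K,x) × C(30−K,15−x) / C(30,15), over all x with |2x − K| ≥ 4.

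For K = 10, this means x ≤ 3 or x ≥ 7:

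P = 2 × (15,504 + 387,600 + 3,488,400 + 15,116,400) / 155,117,520 = 38,015,808 / 155,117,520 = 0.245.

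| Assumed regular users | Split at least as uneven as | Probability |
|---|---|---|
| 6 of 30 | 5:1 | 0.17 |
| 10 of 30 | 7:3 | 0.25 |
| 15 of 30 | 10:5 | 0.14 |

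A 7:3 split means 7/15 = 46.7% regular users in one arm and 3/15 = 20.0% in the other, a gap of 26.7 points. Suppose regular users deliver D percentage points more exposure than the others in either arm. The unadjusted contrast then moves by 0.267 × D, in a direction set by which arm holds the seven. The documents give no value for D.

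**The case against.** The strongest reply is that the contrast can be interpreted without a baseline. Therapists are randomised, and TAU therapists receive no instruction on treatment content (C.7.f). The coded TAU rate therefore estimates what these therapists do without the app. High exposure in both arms points to existing practice; low exposure in both points to no app effect. This stands. A reader might infer that dilution would go unseen, or that the data could not tell an ineffective app from therapists who already used exposure. The coding provisions do not support either inference. A baseline adds an imbalance check, precision and a description by prior use; the comparison does not depend on it.

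Second, the filter is nowhere withdrawn, and several passages presuppose that treating therapists took the survey: the CBT-opposition exclusion in C.4.b and the repeat wording in C.9.e and 4.1.1.b. C.9 also says that all measures in Trials 2 and 3 are taken before and after treatment except as noted. So a flat statement that prior use is not collected goes too far. What stands is that no section expressly provides a linkable measure for directly recruited therapists.

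Third, survey-center custody does not block screening. Under 4.1.2.a the team identifies eligible respondents from de-identified data and the center then releases names. Custody limits linkage for analysis, not selection.

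Finally, C.10.a calls the study descriptive and unpowered, and C.10.b.2 calls the group tests exploratory. That limits the weight of the point but does not remove it.

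**Conclusion.** The point holds as an inconsistency to reconcile and a cheap improvement to make. The filter in C.6.b, C.7.a, 4.1.1.c and the survey part of C.3.a.4 does not reach the Trial 2 route, criteria or telephone screen. A linkable record of prior exposure use before randomisation and training is not expressly planned. The consequence is limited to two things: baseline comparability on prior use cannot be checked, and variation of the app's effect with prior use cannot be described.

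The chance of a marked imbalance is roughly 14% to 25% across the three assumed numbers of regular users with equal allocation. Its effect on the contrast cannot be given as a number, because D is unknown.

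Two further readings should be resisted. One might infer that a stated fraction of the contrast, such as a third, would be lost; any such figure needs assumed exposure rates and an assumed number of regular users in TAU. One might also infer that the later route makes C.8.c wrong where it says "the experimental treatment will be implemented by community therapists recruited from a large geographical area". The documents do not show that the Mayo Clinic Health System or the partner organisations lie outside shortage areas, and C.8.c speaks of such areas only as a particular focus.

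**What to change.** 1. Give Trial 2 therapists the existing Phase I practice items and the exposure-beliefs questionnaire at therapist consent, before randomisation and training. Make the exposure item record frequency: C.9.e describes use or non-use, whereas 4.1.1.b refers to frequency. Store the answers under the therapist's study code so that they can be linked.
2. Report prior exposure use by arm. In the exploratory exposure comparison of C.10.b.2, use it as a covariate or show results descriptively by prior use.
3. Reconcile C.3.a.4 (survey route), C.6.b, C.7.a and 4.1.1.c with the later Trial 2 route in C.3.a.4, the criteria in C.4.a and C.4.b, and the C.7.b screen. Either apply the infrequent-use focus to Trial 2 therapists or stop citing it as a mitigation.

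The cost is protocol wording and a survey that 4.1.1.c puts at 20 to 30 minutes, or 10 to 15 therapist-hours in all for 30 therapists (30 × 20 min = 600 min; 30 × 30 min = 900 min). Enforcing the filter could also reduce the number of eligible therapists; collecting and reporting prior use would not.

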Trial 1. In Trial 1 (Acceptability) we will gather acceptability and usability data from up to 30 therapists. After being consented therapists will complete a packet of information about how they treat child anxiety and their beliefs about treatment related issues. Each therapist will then receive training from a study intervention specialist on how to use Mayo Clinic Anxiety Coach. The therapists will be given access to use Mayo Clinic Anxiety Coach and be given an iPod Touch and can incorporate it into their practice as they desire for a period of six months during which time the therapists will have access to the intervention specialist to answer questions about how to use the application. To protect patient confidentiality, the system will generate numerical identifiers (e.g. Patient #1) and therapists will only be able to enter ages into the system, rather than full names and birthdates. Therapist will be asked to complete questionnaires about how they treat child anxiety and their beliefs about treatment related issues as well as questionnaires about usability and how they integrated Anxiety Coach into their practice two weeks and six months after completing the training. In addition, data automatically recorded through any use of the application will be analyzed.

Trial 2. In Trial 2 (Increasing Exposure Use) 30 therapists will be randomized to treat 30 children with anxiety disorders with treatment as usual or FTF-AC. (If necessary due to limited therapist availability, therapists randomized to TAU will treat a second patient with FTF-AC). Therapists and patients/parents will be consented. Data collection will include questionnaires completed by therapists, patients, and parents before and after treatment, as well as audio recordings of sessions, and data automatically saved by the application.

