C.5.e. Treatment as usual (TAU). The control condition in Trial 3 will consist of having the family participate in the existing clinical services offered by the therapist over the 12-week period. After 12-weeks they will be asked to sign a release of information to have the any outside treatment records sent for review by the study staff. The records will be coded for treatment components. As the post-study evaluations, patients in the TAU condition will receive Anxiety Coach and be offered additional treatment as needed.

C.6. Design Considerations

C.6.a. Justification of Experimental Design. The use of three conditions across two trials allows for an examination of the effects of *Anxiety Coach* and direct therapist contact. Specifically, the **TAU vs. FTF-AC comparison** provides an estimate of the feasibility and palatability of *Anxiety Coach* to therapists, a measure

of the extent to which the application facilitates therapists' use of exposure-based methods, the usefulness of *Anxiety Coach* for disseminating evidence-based CBT methods to community therapists, and its value for facilitating treatment adherence among patients with anxiety disorders. Randomizing therapists/patients to one of two conditions removes the potential for bias to affect recruitment, keeps the evaluators blind to experimental condition, removes concerns with order effects, and allows for the more patients to be treated simultaneously thus decreasing the length of the study. **The MC-AC vs. TAU comparison** provides an estimate of the feasibility as well as the impact on acceptability and outcome of using *Anxiety Coach* with limited direct therapist contact as a method for extending treatment outside of the brick and mortar mental health settings. To increase the real-world generalizability of the study, the study will not pay for therapy, but patients in all conditions will be reimbursed for participation in assessments and will be allowed to keep the iPod Touch.

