If therapists in Trial 1 choose to use Anxiety Coach in their practice during, those patients will not be engaged in any research activities. In order to use the application the patient must agree to the terms of use that explain what data Mayo Clinic collects and how these data are used.

C.7.e. Treatment Assignment. For Trial 2, therapists will be randomized to either TAU or FTF-AC after they are consented. The therapist will then offer participation to the next patient they see likely to qualify. (If needed, the second patient treated by a therapist randomized to TAU will be enrolled in the FTF-AC condition.) This format clearly differentiates the therapists' participation in the study from the patients' participation. To limit bias in enrollment, neither patients nor the independent evaluators will be aware of therapeutic condition at the time of enrollment. Treatment in each condition can begin within 1 to 2 weeks of the evaluation as soon as the patient has completed the study evaluation. All patients will be informed that participation in the study includes the possibility of enrollment into either of two conditions. If patients discontinue treatment prematurely, before the sixth session, they will not be replaced with another patient. Instead efforts will be made to complete early withdrawal post-treatment evaluations on all enrollees and the frequency of premature discontinuation will be compared between conditions. For Trial 1, the therapists will have access to the Anxiety Coach application and can use it as they choose in their clinical practice. For Trial 3, treatment assignment will occur following consent and the pre-evaluation is completed.

C.7.f. Therapists, Treatment Integrity and Competence. Therapists in Trials 2 and 3 will provide treatment. To determine the success of creating conditions with distinct therapist behavior, all sessions and communication in each condition will be recorded and coded for use of exposure and other interventions. In the TAU condition, the therapist will not receive any instruction regarding the content of treatment. In all three conditions across the two trials the intervention specialists or the PI will monitor and support the therapists' compliance with guidelines. The intervention specialists have highly developed therapeutic skills, at least five years' experience providing CBT to children with anxiety disorders and their families, extensive one-on-one

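### Trial 2 randomizes the therapist before that therapist approaches a child, does not say the arm is withheld, and may assign second patients by rule, so C.6.a's claims are too strong for patients

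*Protocol*

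**What the plan says.** Protocol C.3.b sets the size of Trial 2: "30 therapists will be randomized to treat 30 children with anxiety disorders with treatment as usual or FTF-AC". C.7.e sets the order of events: "therapists will be randomized to either TAU or FTF-AC after they are consented. The therapist will then offer participation to the next patient" who, in the therapist's view, will probably meet the criteria. C.4 confirms that therapists recruit the patients at their initial evaluation, and that study staff screen and consent them.

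C.7.e gives its reason for this order: "This format clearly differentiates the therapists' participation in the study from the patients' participation". On masking it says: "To limit bias in enrollment, neither patients nor the independent evaluators will be aware of therapeutic condition at the time of enrollment". The other randomized comparison uses a different order: "For Trial 3, treatment assignment will occur following consent and the pre-evaluation is completed".

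C.3.b and C.7.e also provide for a shortage of therapists. If needed, "the second patient treated by a therapist randomized to TAU will be enrolled in the FTF-AC condition".

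C.6.a describes what the design achieves in stronger terms: "Randomizing therapists/patients to one of two conditions removes the potential for bias to affect recruitment". It adds that this "removes concerns with order effects".

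**The concern.** The person who decides which child to approach has already been randomized, and the documents do not say that this person is unaware of the result. A therapist who knows the arm may, without intending to, apply a different standard of likely eligibility under TAU than under FTF-AC. The exclusions in C.4.b leave room for judgement at a first evaluation: oppositional defiant disorder, major depression, and a previous adequate course of CBT.

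Second patients raise a separate problem. Their arm follows from a rule rather than from chance, and for their therapist FTF-AC always comes after TAU. Pooling them with randomized patients would mix a non-randomized, fixed-order group into the comparison. C.10.c makes intention to treat the principal analysis set, and 4.1.2.b includes everyone randomized, but neither says how rule-assigned patients are handled.

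At stake are the effect estimates that C.10.b.2 sets out to generate for planning a powered trial. No confirmatory test depends on them.

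**Working it through.** **1. Order and masking.** The two randomized comparisons, from C.7.e, C.7.d and C.4:

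| Step | Trial 2 | Trial 3 |
|---|---|---|
| Randomization | After therapist consent, before any patient is approached | After patient consent and pre-evaluation |
| Who is stated to be unaware at enrollment | Patients, independent evaluators | Not an issue: the arm does not yet exist |
| Who chooses whom to approach | The randomized therapist | Choice precedes assignment |

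The reason given for the Trial 2 order, keeping therapist and patient participation distinct, does not require telling the therapist the arm before the offer.

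**2. What each safeguard covers.**
- At the offer: the next-patient rule (C.7.e) and the prepared script (4.1.2.a). The rule still passes through the therapist's judgement of likely eligibility.
- After the offer: staff screening and consent (C.4) and eligibility set by a blinded evaluator (C.7.d). These can reject a child who was offered the study but cannot recover one who was not.
- In the records: the Screening Log counts ineligible callers (C.7.c), and tracking covers screening, eligibility and enrollment (4.1.2.a). A child never offered the study leaves no trace.
- In the analysis: ANCOVA for exposure use controls for diagnosis and symptom severity. Symptoms are compared as change by repeated measures ANOVA, with no covariates listed (C.10.b.2). Neither deals with unmeasured traits.

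**3. How many patients could be assigned by rule.** The only planned figures are 30 therapists and 30 patients (C.3.b). The rest is illustration, assuming 1:1 randomization of therapists, second patients used only to reach 30, and at most two patients per therapist (C.5, C.7.e). For T therapists, second patients s = min(30 − T, T/2), FTF-AC patients = T/2 + s, and rule-assigned share = s / (T/2 + s).

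| T | s | TAU | FTF-AC | Rule-assigned share of FTF-AC |
|---|---|---|---|---|
| 30 (plan) | 0 | 15 | 15 | 0/15 = 0% |
| 24 | 6 | 12 | 18 | 6/18 = 33% |
| 20 | 10 | 10 | 20 | 10/20 = 50% |

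Under these assumptions 50% is the maximum. Below 20 therapists the share stays there and the total falls short of 30 (T = 18: 9 + 9 + 9 = 27).

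**4. Precision lost by leaving second patients out.** The standard error of a mean difference, in SD units with independent patients, is √(1/n₁ + 1/n₂).
- T = 30: √(1/15 + 1/15) = 0.37, with nothing to leave out.
- T = 24: first patients only √(1/12 + 1/12) = 0.41; pooled √(1/18 + 1/12) = 0.37.
- T = 20: first patients only √(1/10 + 1/10) = 0.45; pooled √(1/20 + 1/10) = 0.39.

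Each second patient shares a therapist with a TAU patient, so with f FTF-AC and t TAU patients the pooled variance becomes 1/f + 1/t − 2sρ/(ft). For an assumed within-therapist correlation ρ of 0 to 0.2, the pooled standard error runs from 0.373 to 0.357 (T = 24) and from 0.387 to 0.361 (T = 20).

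**The case against.** The case for leaving the plan alone is substantial. The study is not powered for group differences and its analysis is mainly descriptive (C.10.a); group tests are exploratory (C.10.b.2). Therapists consent before they are randomized, so their own recruitment is protected. They are also the randomized unit for the exposure comparison, which adjusts for diagnosis and severity. C.7.e itself claims only to limit bias. All of this stands and holds the severity down. It does not make C.6.a's wording correct for patients.

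Three stronger readings are tempting and should not be drawn:
- **That therapists are told their arm before they approach a child.** The documents do not say so. C.5.a requires training only before each patient starts treatment, which is compatible with later disclosure, and the Use and Procedures Manual described in C.3.a.2 may settle the matter. The gap is that the protocol is silent. Likewise, a second patient's arm is predictable under the rule, but no text says when the therapist learns that the rule will be used.
- **That a third to a half of FTF-AC will be non-randomized.** The plan is 30 therapists, which gives 0%. The other shares are illustrations. C.5 allows any therapist one or two patients, so second patients of FTF-AC therapists would lower them.
- **That the SAP already shows Trial 2 baseline symptoms by arm.** The SAP never names Trial 2. Its family interviews match the Phase I open pilot (C.3.a.3, C.10.b.1), so it should not be cited either way here.

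**Conclusion.** The point holds, at minor to moderate severity. For patients in Trial 2, C.6.a claims two properties that the design in C.7.e does not secure: freedom from recruitment bias, because the arm is not stated to be withheld from the recruiting therapist; and freedom from order effects, because rule-assigned second patients always follow a TAU patient. The recruitment claim is sound for therapists, and the order-effects claim is sound for first patients.

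The documents give no figure for the size of any recruitment bias and none is assumed here. They do not show that bias will occur. The second-patient problem arises only if the shortage rule is used, and the shares above rest on the assumptions listed with them.

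**What to change.** 1. **C.7.e.** Keep therapist randomization where it is, but release the arm to the therapist only once the patient is enrolled as C.7.d and 4.1.2.a define it: eligibility confirmed, baseline evaluation done, and signed consent/assent received and signed by staff. The end of the videophone visit is too early. Families who do not post the forms become screen failures whose data are excluded, so a family that had learned the arm could still leave because of it. Someone other than the independent evaluator should release the arm. The technology call (FTF-AC) and training then follow, before treatment starts, where C.5.a already places them. If the manual already works this way, say so in C.7.e.
2. **Analysis.** Make the TAU versus FTF-AC comparison on randomized first patients only. Report rule-assigned second patients separately.
3. **Therapists who already know their arm.** Keep a short log of likely-eligible children seen and whether each was offered the study. Show baseline characteristics by arm.
4. **C.6.a.** For patient recruitment, replace *removes* with *limits*. Exclude second patients from the order-effects statement.

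**Cost.** Mostly text, plus a short log. Waiting for mailed forms tightens the one-to-two-week interval between evaluation and treatment (C.7.e, C.7.g), into which the call and the 30 to 90-minute training must also fit. It pulls against the aim in 4.1.2.a of minimizing delay, and the protocol gives no time for return of forms. Leaving out second patients costs precision only if they are used: a standard error of 0.41 instead of 0.37 SD with 24 therapists. No extra patients are needed.
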